AF is a symptom of underlying cardiovascular risk factors and a marker of increased mortality and morbidity. We need to shift our focus to the treatment of these underlying risk factors in patients with AF. Diet, exercise, and risk factor management can be used to modify these risk factors both in the short term, and potentially with sustained effect. This study employs a randomized design to test a six-month supervised intensive exercise, diet, and risk factor management program, followed by a six-month home-based exercise and diet program. Based on previous studies, we hypothesize that this should lead to an improvement in cardiovascular risk factors, a reduction in AF burden, and possible improvements in left atrial remodeling.

3. Hypotheses:

- i) Patients with paroxysmal non-valvular AF that complete a supervised six-month program of exercise, diet, and life style modification will exhibit reduced recurrent AF and reduced cardiovascular risk factors when compared to a similar group of patients who receive usual care.
- ii) The intervention group will show improvements in physical fitness, cardiovascular risk factors, and AF symptoms and severity at both the six-month and one-year follow-up assessments compared to the usual care group.
- iii) A reduction in medication costs and emergency room visits will help offset the cost of the intervention.

4. Objectives: The objectives of this study are to demonstrate changes in symptoms and severity of AF following an exercise, diet, and risk factor modification intervention in patients with AF. Demonstrating that a comprehensive cardiac rehabilitation program is feasible and cost-effective will help us design a future larger-scale, multi-centre study.

i) Primary outcomes include:

- a. Burden of AF, including both frequency and symptoms.
 - i. The frequency of AF will be measured with 48-hour Holter monitor recording, looking at percent of time in AF at baseline, six months and one year follow up.

- ii. Symptoms of AF will be assessed using the Canadian Cardiovascular Society Severity in Atrial Fibrillation Scale (CCS-SAF) (31), and the Atrial Fibrillation Symptom Severity Scale (AFSS) (32); both are validated tools to assess burden of AF symptoms.
- iii. The 36-item Short Form Survey Instrument (33) and the EQ-5D-3L (34) will be used to measure quality of life.

ii) Secondary outcomes include:

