- a. Left atrial remodeling will be measured by LA volume index, diastolic function grade, and estimate of LA pressure via echocardiography at baseline and one year follow-up.
- b. Cardiovascular risk factors will be compared at baseline, six months and one year. These include: Systolic Blood Pressure, Hemoglobin A1C (marker of average blood sugar over 3 months), body mass index, waist circumference, and low density lipoprotein (LDL cholesterol), apnea hypopnea index (AHI), and fitness classification (metabolic equivalents (METS) achieved on exercise stress test).
- c. Using pharmanet data, total cost of all medications and specific cost for antiarrhythmic agents, antihypertensive agents, diabetes and cholesterol lowering medications will be recorded and compared at baseline and one year. Hospital Emergency visits will also be compared.

5. Methodology

5.1 Proposed Study Design: This is a parallel-group randomized controlled trial. Consecutive patients meeting eligibility criteria that are seen for routine cardiology follow-up, or those referred by family physicians, will be invited to participate in this study. Patients who accept the possibility of a year-long diet counseling and exercise program will be randomized and stratified to ‘control arm’ *versus* ‘intervention arm.’ Forty patients will be randomized to control arm and 40 patients randomized to the intervention arm. Intervention will include Phase 1, a six month program including three months of diet counseling combined with home exercise, followed by three months (starting at week 13) of an in-hospital, Cardiac rehabilitation exercise program. Phase 1 also includes risk factor management by an internist who specializes in cardiovascular risk factors. Phase 2 of the intervention will include six months of home-based maintenance exercise and diet (starting at week 25). Assuming approximately 40% of eligible patients agree to participate (based on our experience that there is a high willingness to participate in both research studies and the cardiac rehabilitation program), and given that we were able to recruit 200 research participants in one year for a previous study (35), we estimate that it is feasible to recruit a total of 80 participants over a three to six month period.

5.2 Participants: Patients will provide written, informed consent. All study procedures will be reviewed and approved by the UBC Clinical Ethics board and the VCH operational approval process.

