Inclusion Criteria: Patients with paroxysmal, non-permanent, non-valvular AF who have a $BMI \geq 27 \text{ kg/m}^2$, or central obesity using abdominal circumference with ethnicity-specific values recommended by Canadian diabetes association (36); plus one of hypertension, diabetes, moderate or severe sleep apnea, or consumption equal to or greater than three glasses of alcohol per day. Participants must be over 18 years of age and under 75 years.

Exclusion Criteria: Patients with permanent AF, estimated survival less than 2 years, left ventricular ejection fraction $< 40\%$, and/or prior cardiac valve surgery. Other exclusions include: inability to walk on a treadmill, defibrillator, entry exercise test positive for ischemia (37), and/or absolute and relative contraindications to exercise testing (37).

5.3 Study Procedure: All participants will undergo baseline, maximal effort exercise testing described in data collection section 5.4. Peak heart rate (HR_{peak}), total METS, and Borg rating of perceived exertion scale will be recorded (37). Maximal exercise tests will be repeated at six months and one year in all participants. All participants in the intervention and control arms will be screened for obstructive sleep apnea with a home sleep apnea test (level three study). [name] (Respirologist at Richmond hospital) will assess any patients with at least moderate sleep apnea, an apnea hypopnea index over 20. [name] has expertise in sleep apnea and is a co-investigator of this study. CPAP will be recommended and for one year for patients with apnea hypopnea index of > 30 , or > 20 with excessive day time sleepiness. CPAP machines will be loaned by the sleep clinic to patients who do not have insurance coverage for one year. LA volume index, pressure and grade of diastolic dysfunction will be measured by echocardiography at baseline and one year. The same technician will perform all echocardiograms using the same echocardiogram machine, and one cardiologist blinded to participant’s study arm will review the results.

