5.4 Data Collection

All measurements (save demographics and medical history) will be collected at baseline, six months, and one year in both groups.

1. Patient demographics: age, sex, ethnicity, education, income, and living situation.
2. Medical history: medications and cost; hospital emergency visit and admission < 1yr, known coronary artery disease defined by prior myocardial infarction or presence of 50% stenosis on CT or invasive angiogram; admission for heart failure, prior stroke; average daily glasses of alcohol, smoking status (including frequency and amount); the Canadian Cardiovascular Society Severity in Atrial Fibrillation (CCS-SAF) Scale, (31) the Atrial Fibrillation Symptom Severity Scale (AFSS) (32), the 36-item Short Form Survey Instrument (33) and the EQ-5D-3L (34).
3. Anthropometrics: Body mass index (BMI), waist circumference, neck circumference, modified mallampati score (41) and blood pressure.
4. Blood work: Hemoglobin AIC, total cholesterol, creatinine, low-density lipoprotein, high-density lipoprotein, triglycerides, ALT, c-reactive protein, electrolytes, and brain natriuretic peptide.
5. Level 3 home sleep study: Apnea-hypopnea index, minimum saturation, and time spent with saturation < 90%, Epworth Sleepiness Scale (42).
6. Godin's leisure time physical activity measure will be used measure baseline physical activity levels (43).
7. Exercise Stress Test at maximal effort: Maximum METs achieved, peak heart rate, and rating of perceived exertion.
8. 48-hour Holter monitor: 48-hour heart rhythm monitor to determine frequency and duration of AF measured as the percent of time in AF.
9. Echocardiography at base line and one year: measurements: LA volume, LA pressure, diastolic function, grade, calculated biplane LVEF, and left ventricular hypertrophy.

All data sheets are attached in section 9 of the application. There is a data sheet for each: sleep study, echo, blood work, stress test, physical exam, and Holter monitor.

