5.4 Data Analysis (and sample size)

This is a parallel, randomized control study. The researcher analyzing results will be blinded to the patient's group. A statistician will be hired to analyze data and a statistician from C2E2 (UBC) has reviewed the study design. Normally distributed data will be analyzed using repeated measures analysis of variance (ANOVA) to calculate changes over time (baseline, six-months, one-year) within each group. Between groups analyses on differences from baseline will be analyzed using independent *t*-tests. Statistical significance will be set *a priori* as *p*<.05. Continuous variables will be described by group using mean (SD) (or median (P25, P75) if the data are skewed); and categorical variables will be described by frequency (percent).

To calculate effect size for the intervention group, we considered the moderate effect sizes reported in exercise studies measuring cardiorespiratory changes (e.g., Huang et al. (2016) (40) reported a moderately high effect size of 0.64 for aerobic changes following an exercise program in older adults). Using G-power software (*alpha* = .05), the

sample size required to achieve 80% power to detect an effect is 22 per group (two-tailed, or repeated measures design) (44). Based on the data from Malmo and colleagues (26) reporting a large effect size (1.0) for the difference in time spent in AF pre- and post-exercise, a sample size of less than 10 participants would achieve a power of 80%. The AF studies to-date report low attrition rates. For example, Pathak et al. (19) reported 10% attrition in the risk factor intervention group, and Malmo et al.(26) reported a 0% attrition in the three-month interval-training program. Given that the Richmond Cardiac Rehabilitation program similarly reports low drop-out rates (of approximately 2%), we have allowed for greater than 10% attrition. Including 40 participants in the intervention arm, and 40 participants in the control arm will allow for more than 10% drop out while still maintaining adequate power to detect an effect.

6. Summary and Impacts on Practice

Richmond has experience in recruiting patients with AF, cardiac rehabilitation, and bariatric diet therapy program. Our Richmond team of specialists, combined with strong partnerships with our colleagues at VGH that have experience with research trials will help guide us in implementing a successful research project.

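### Percent time in AF is compared between arms only by a t-test on change; adjusting for the baseline Holter would be more precise, and no test is named for skewed values

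*Combined protocol and SAP*

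**What the plan says.** Section 4 (Objectives) lists AF frequency first among the primary outcomes, "measured with 48-hour Holter monitor recording, looking at percent of time in AF", at baseline, six months and one year. Item 8 of section 5.4 (Data Collection) repeats the measure: "48-hour heart rhythm monitor to determine frequency and duration of AF measured as the percent of time in AF". There is one recording per visit.

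Section 5.4 (Data Analysis and sample size) gives two inferential methods:

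- Within each arm: "Normally distributed data will be analyzed using repeated measures analysis of variance (ANOVA) to calculate changes over time".
- Between arms: "Between groups analyses on differences from baseline will be analyzed using independent" *t*-tests.

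Skewed data are mentioned only for description, where the median and quartiles replace the mean and SD. No covariate adjustment, rank test, transformation or other method for non-normal values appears.

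Eligibility in section 5.2 begins "Patients with paroxysmal, non-permanent, non-valvular AF who have a" raised BMI or central obesity; no minimum AF burden is required. Section 5.1 says that patients "will be randomized and stratified to" the two arms, but names no stratification factor.

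On sample size, section 5.4 takes an effect size of 1.0 for time in AF before and after exercise in an earlier interval-training trial and says that "a sample size of less than 10 participants would achieve a power of 80"%.

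**The concern.** Each visit supplies a single 48-hour sample of an intermittent arrhythmia, in patients who need no minimum burden to enter. Percent time in AF is therefore likely to be noisy, to contain many zeros and to be skewed. This is an inference: the documents give no share of zeros, no SD and no baseline/follow-up correlation.

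A change score carries the sampling noise of both recordings. Unless the two are highly correlated, subtracting baseline in full costs precision that adjustment by regression would keep. The only between-arm test uses the change score, and nothing says what replaces it if the values are clearly non-normal.

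The Holter is the trial's only objective measure of AF frequency, and section 4 wants the results to help design a larger multi-centre study. At stake is efficiency: a wider interval, and a greater chance of missing a real reduction, than the same data allow.

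**Working it through.** **The plan's own figure.** At effect size 1.0, 80% power and 5% significance:

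- Paired (pre/post) *t*-test: 9.9, so 10 participants two-sided (power is 74.8% with 9); 7.7, so 8 one-sided. The normal approximation, two-sided, is (1.960 + 0.842)²/1.0² = 7.85, so 8.
- Two-arm *t*-test, two-sided: 16.7, so 17 per arm.

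The stated figure of fewer than 10 is thus reproduced only as a single-group pre/post number. It does not size the planned comparison of arms.

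**Closed form.** Let percent time in AF have the same SD, σ, at both visits, with correlation r within an arm.

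- Variance of the change score: 2(1 − r)σ².
- Variance after linear adjustment for baseline: (1 − r²)σ² = (1 − r)(1 + r)σ².
- Ratio, ANCOVA to change score: (1 + r)/2, which is below 1 for every r below 1.

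Ten per cent attrition leaves 40 × 0.9 = 36 per arm.

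| r (assumed) | Variance ratio (1+r)/2 | Participants needed on change, relative to ANCOVA, 2/(1+r) | 36 per arm on change is worth, under ANCOVA |
|---|---|---|---|
| 0.1 | 0.55 | 1.8 | 19.8 per arm |
| 0.3 | 0.65 | 1.5 | 23.4 per arm |
| 0.5 | 0.75 | 1.3 | 27.0 per arm |
| 0.8 | 0.90 | 1.1 | 32.4 per arm |

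Below r = 0.5 the change score is noisier than the follow-up value alone, since 2(1 − r) exceeds 1.

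**Simulation with zeros and skew.** All inputs here are assumed. There were 36 per arm and 4,000 trials per setting. The chance of any AF in a window varied between patients (beta distribution, mean 0.2, 0.3 or 0.5), and burden given AF was logit-normal with a patient effect. Control-arm r came out at 0.09 to 0.53, and the change was exactly zero in 28–75% of patients.

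| Assumed effect | Power, *t*-test on change | Power, ANCOVA | Power, rank ANCOVA |
|---|---|---|---|
| Chance of any AF halved | 11–29% | 16–42% | 21–65% |
| Duration only (−1 on the logit scale) | 9–22% | 10–40% | 5–15% |
| Both | 17–53% | 30–86% | 24–79% |

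Type I error was 4–5% for each method. The ends of paired ranges need not come from the same setting. Setting by setting, ANCOVA was at or above the *t*-test in all 27; the smallest gap was 0.3 points, a tie within simulation error.

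Rank ANCOVA fell below the planned *t*-test when only duration changed. With a larger duration effect (−1.5 logit) the ranges were 13–37% for the *t*-test, 18–72% for ANCOVA and 5–24% for rank ANCOVA.

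**Choice of p-value.** ANCOVA with a permutation p-value (499 permutations, 1,500 trials, with settings at r about 0.8 added) had type I error of 4–6%. Its power exceeded the *t*-test on change in all 36 effect settings, by about 1 to 39 points. Heteroscedasticity-robust (HC3) standard errors were conservative and fell below the *t*-test in one setting (8% against 10%).

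**The case against.** The planned test has no validity defect: in a randomised trial a *t*-test on change is an unbiased comparison of arms. The study is framed as groundwork for a larger one, section 6 already says that a loop recorder would measure recurrence better, and a statistician is to be hired. All of that is true. It does not justify giving up precision that costs nothing to keep, and the method for a primary outcome should be fixed before the data exist.

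Every input that sets the size of the gain is assumed. If r is high, the closed form shrinks to a factor of 1.1. This stands: the direction is algebra, the size is not known.

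The simulated gains also exceed what the closed form can give. Under equal variances and a normal approximation, the largest possible gain in power is about 25 points at r = 0.1, 12 at r = 0.5 and 5 at r = 0.8. The simulated effects are multiplicative, so they also shrink the treated arm's follow-up variance and lower its correlation with baseline. Part of the larger gains comes from that assumed form of effect. This stands too, and the two sets of results should be read separately.

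Finally, a permutation p-value beside an ordinary confidence interval can disagree; in simulation the ordinary ANCOVA interval covered about 90–96%. One line naming the interval method settles this.

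**Conclusion.** The concern holds as a matter of efficiency, and the plan should be changed. The only between-arm test for percent time in AF is less precise than a baseline-adjusted analysis of the same data, and no test is named for non-normal values. At r = 0.1 to 0.5 the loss is equivalent to analysing about 20 to 27 per arm instead of 36; at r = 0.8 it is about 10%. These figures assume equal variance at both visits and a linear relation to baseline. That r is low, and that zeros are common, is plausible but not documented, so confidence in the size is medium.

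Power remains low for every method in many of the simulated settings: adjustment recovers part of the loss, not all of it. The sample-size remark for time in AF is mislabelled, but this does not undermine the planned size: 40 per arm exceeds 17 if an effect of 1.0 does apply between arms.

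**What to change.** In section 5.4 (Data Analysis), for percent time in AF at six months and at one year:

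1. Replace the *t*-test on change with a pre-specified ANCOVA of the follow-up value on arm, baseline percent time in AF and any stratification factors, and name those factors.
2. Take the p-value from permutation of the arm labels, within strata if there are any. Report the adjusted mean difference in percentage points with a 95% confidence interval, for example by inverting the permutation test.
3. As supportive analyses, report the proportion with any AF in the window by arm, and a proportional-odds or rank ANCOVA. A rank method should not be the sole analysis, because it does poorly when only duration falls.
4. State the assumed share of recordings with no AF, the SD and the correlation.
5. Relabel the figure of fewer than 10 participants as a single-group pre/post number, and give 17 per arm as the two-arm requirement at effect size 1.0.

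The cost is wording: the baseline and follow-up Holters are already scheduled. The headline estimate would no longer be the raw difference in change scores, but those can still be described by arm.

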The Legacy trial investigated the effects of diet intervention (20). The study followed 355 participants with Body Mass Index (BMI) 27 kg/m^2 or greater that participated in a weight loss program; 38% of the participants sustained a weight loss 10% of total body weight or greater. Greater than 10% weight loss resulted in a six-fold reduction in the recurrence of AF and improved cardiovascular risk factors compared to those who lost less weight and whose weight loss fluctuated (20).

Obstructive sleep apnea (OSA) is known to be highly prevalent in AF (27). A meta-analysis looking at both cohort and randomized trials of continuous positive air pressure (CPAP) for OSA in patients with AF resulted in a 42% low risk of AF recurrence (28). Thus, CPAP treatment for moderate or greater sleep apnea combined with exercise and diet may improve AF outcomes.

A major limitation of previous AF trials is lack of randomization and short duration of follow-up. In addition, no studies have investigated an intervention program that combines supervised exercise sessions, regular, structured diet and lifestyle education sessions, and risk factor management. There have been no meta-analyses on the effects of exercise and diet on AF symptoms given that there exist only a handful of studies to date. A Cochrane review (29) of randomized controlled exercise interventions in AF patients reported no differences in mortality and quality of life, and reported only small differences in exercise capacity, but the review did not evaluate symptom severity of AF nor did they measure reductions in risk factors commonly associated with AF. The review suggested a need for more randomized clinical trials (given that only six were included in this initial review) (29). Not only are there very few lifestyle intervention studies on AF, no studies have compared a structured in-hospital diet and exercise program *versus* a home-based exercise and diet program. We do not know whether positive effects are sustained once supervised interventions are terminated; nor do we know the necessary intensity to achieve and sustain target reduction in cardiovascular risk, left atrial remodeling, and AF burden.

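### The sample-size section shows no between-arm power for any primary outcome, and at its own effect size of 0.64 the planned test falls below 80% power after 10% dropout

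*Combined protocol and SAP*

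**What the plan says.** Section 4 lists as primary outcomes the percent of time in AF on a 48-hour Holter, the CCS-SAF and AFSS symptom scales, and the SF-36 and EQ-5D-3L. Fitness is among the secondary outcomes: "fitness classification (metabolic equivalents (METS) achieved on exercise stress test".

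Section 5.4, Data Analysis (and sample size), compares arms by independent t-tests on differences from baseline, with significance at 0.05. It gives two justifications for the sample size.

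- **Fitness.** A study of older adults "reported a moderately high effect size of 0.64 for aerobic changes following an exercise program in older adults". With alpha 0.05 in G*Power, the "sample size required to achieve 80% power to detect an effect is 22 per group". The design is described only as "two-tailed, or repeated measures design".
- **Time in AF.** The plan cites an interval-training study "reporting a large effect size (1.0) for the difference in time spent in AF pre- and post-exercise", and says that "a sample size of less than 10 participants would achieve a power of 80" percent.

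The section concludes that 40 per arm allows for more than 10% dropout with adequate power retained.

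**The concern.** The trial's main question is whether the arms differ. A sample-size statement for it needs a between-arm difference in change, the SD of that change, and the test that will be used. Neither justification supplies these for a primary outcome. The first concerns a secondary outcome, and its 22 per group looks small for a two-group comparison at 0.64. The second concerns a primary outcome but describes change over time in people who exercised. The symptom and quality-of-life measures have no effect size at all.

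At stake is how the results will be read. Section 4 says the study should help design a larger multi-centre trial. If adequate power is stated without qualification, a non-significant difference in AF burden, symptoms or quality of life carries more weight than 36 to 40 patients per arm can support.

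**Working it through.** **Inputs from section 5.4, Data Analysis:** two-sided alpha 0.05; target power 80%; effect sizes d = 0.64 and 1.0; independent t-test on change from baseline; 40 per arm. Ten percent dropout leaves 40 × 0.90 = 36 per arm.

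**Step 1. Reproduce the plan's figures.** For a paired t-test, power comes from the non-central t with n − 1 degrees of freedom and non-centrality d√n.

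- d = 0.64: n = 21.2, rounded up to 22. At n = 22, non-centrality is 0.64 × √22 = 3.00 and power is 81.7%; at n = 21 it is 79.7%. This reproduces the plan's 22.
- d = 1.0: n = 9.94, rounded up to 10. Power is 74.8% at 9 and 80.3% at 10. The normal approximation gives 8, so the plan's figure of under 10 is close for a paired test.

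The plan does not name the test behind the 22. A between-factor repeated-measures ANOVA with three visits and f = 0.32 also gives 22 per group, but only with a correlation of about 0.3, which the plan does not state; at 0.5 it gives 27. It is not the planned between-arm analysis either.

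**Step 2. Apply the planned test.** For an independent t-test with n per arm, degrees of freedom are 2n − 2 and non-centrality is d√(n/2). At d = 0.64 the solution is n = 39.3, so 40 evaluable per group. Allowing for 10% dropout requires 40 / 0.90 = 44.4, so 45 per arm.

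| Evaluable per arm | Non-centrality at 0.64 | Power at 0.64 |
|---|---|---|
| 22 | 2.12 | 54.5% |
| 36 | 2.72 | 76.4% |
| 39 | 2.83 | 79.7% |
| 40 | 2.86 | 80.7% |

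Forty per arm just meets the target with complete data; losing one patient per arm takes it below 80%.

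**Step 3. What 40 (36) per arm can detect.** The smallest difference with 80% power is 0.63 (0.67) SD of change. The 95% confidence-interval half-width is t × √(2/n): 1.991 × √(2/40) = 0.45 SD, and 1.994 × √(2/36) = 0.47 SD.

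**Step 4. Time in AF.** If 1.0 were the between-arm difference in SD of change, 17 per arm would suffice, and power would be 99.3% at 40 and 98.7% at 36. The pre/post figure carries over only if controls do not change on average and the SD behind the 1.0 matches the SD of change in this trial. The plan states neither. Controls receive guideline AF therapy, a step tracker and an activity handout (5.3.1), and the same sleep-apnea treatment (5.3 and 5.3.2), so some improvement among them is possible.

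**Step 5. Assumed smaller effects.** The documents give no values for these; the range is only illustrative.

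| Assumed difference (SD) | Power, 40 per arm | Power, 36 per arm |
|---|---|---|
| 0.2 | 14% | 13% |
| 0.3 | 26% | 24% |
| 0.4 | 42% | 39% |
| 0.5 | 60% | 55% |

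**The case against.** The strongest reply is that the plan does address a primary outcome, since the 1.0 is for time in AF. There is also room for that effect to shrink: at 0.70 between arms, power would still be 87% (83%). This stands in part. A reader might infer that the power claim rests on fitness alone, and the documents do not support that. What is missing is any argument that a pre/post effect is an arm difference.

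A reader might also infer from the plan's own background that effects will be small. Current state of knowledge cites a review of randomised exercise trials in AF that "reported no differences in mortality and quality of life, and reported only small differences in exercise capacity". That is too weak to establish low power. The review had six trials, covered exercise only whereas this trial adds diet and risk-factor management, and did not assess AF symptom severity. The plan puts no number on small, and exercise capacity is not a primary outcome.

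Nor can the 0.64 be dismissed because its source programs averaged 23 weeks and supervised exercise here runs only in weeks 13 to 24. Section 5.3.2 prescribes home exercise from week 2, so the total duration by six months is similar, and the plan does not say the source programs were supervised throughout.

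Finally, no passage says that a null result will be taken as no effect, and the plan commits to publishing whatever the direction. The risk of misreading is real, but it is not a stated intention.

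**Conclusion.** The point holds in a limited form. No between-arm power is shown for any primary outcome: one justification concerns a secondary outcome, the other is a change over time, and four primary measures have no effect size. At the plan's own 0.64, the planned test has 80.7% power with 40 per arm and 76.4% with 36, so the dropout statement fails by about 4 percentage points against the 80% target.

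This assumes a two-sided independent t-test at 0.05, equal SDs in the arms, approximately normal changes and exactly 10% dropout. That the 22 is a paired figure is inferred from its reproducing; the 40 per group does not depend on that inference.

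It would go too far to call the trial underpowered for its primary outcomes. For time in AF, power could be high if the between-arm effect is near 1.0. For symptoms and quality of life, the documents give no effect from which to judge.

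**What to change.** Keep 80 patients and change the wording of section 5.4, Data Analysis (and sample size):

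- Label the 22 per group as a within-group figure for fitness, a secondary outcome, at 0.64. Name the test used, after checking it against the G*Power record.
- Keep the time-in-AF sentence, label it as a within-group pre/post figure, and correct the number to about 10 for an exact two-sided paired test.
- Replace the closing power sentence with: *40 per arm (36 after 10% dropout) gives 80% power for a between-arm difference of 0.63 (0.67) SD of change from baseline in an outcome analysed by the independent t-test; at 0.64 SD power is 81% (76%); smaller effects may be missed.*
- State that a non-significant primary result will be read from its confidence interval (half-width about 0.45 to 0.47 SD).
- If power at 0.2 to 0.5 SD is shown, mark that range as assumed.

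The cost is a few sentences and a less favourable power statement. No patients, visits or procedures are added. Holding 80% power at 0.64 after 10% dropout would instead take 45 per arm; the rewording does not require this.

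### The 22 per group does not fit the planned between-arm t-test, which needs 40 per arm at 0.64 SD of change, so the dropout allowance is unsupported

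*Combined protocol and SAP*

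**What the plan says.** Section 5.4 (Data Analysis and sample size) plans two analyses. Repeated measures ANOVA is used inside each group to describe change over the three visits. For the comparison of the arms, the plan is: "Between groups analyses on differences from baseline will be analyzed using independent" t-tests. Hypotheses i and ii in section 3 both set the intervention against usual care, so the second analysis is the one that answers them.

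The sample-size paragraph begins: "To calculate effect size for the intervention group, we considered the moderate effect sizes reported in exercise studies measuring cardiorespiratory changes". It takes 0.64 from a study of aerobic change after an exercise program in older adults, sets alpha at 0.05, and concludes that the "sample size required to achieve 80% power to detect an effect is 22 per group (two-tailed, or repeated measures design").

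For time in AF it takes an effect of 1.0, described as a before-and-after difference, and says that "a sample size of less than 10 participants would achieve a power of 80" per cent. Its conclusion is that 40 per arm "will allow for more than 10% drop out while still maintaining adequate power to detect an effect".

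The two effects concern outcomes of different rank in section 4. Fitness is secondary: "fitness classification (metabolic equivalents (METS) achieved on exercise stress test"). Time in AF is primary, measured by Holter monitor, "looking at percent of time in AF at baseline, six months and one year follow up".

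**The concern.** Both effect sizes are introduced as changes within people who exercised. No between-arm difference, SD of change or baseline to follow-up correlation is given. A two-sample comparison at a given standardised effect needs nearly twice as many patients per arm as a paired test needs in total, because the control arm's mean change also has to be estimated. If the 22 is a one-group figure, the apparent reserve between 22 and 40 is not a reserve for the planned test, and the dropout statement rests on nothing.

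The stake is how the fitness comparison is read. A null result would be judged against an 80% power that belongs to another test. Section 4 also says the trial is meant to inform a larger multi-centre study, and a one-group size labelled as per group could be carried into it.

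**Working it through.** **Inputs from section 5.4:** alpha 0.05, two-tailed; power 80%; effect 0.64 (fitness) and 1.0 (time in AF); 40 randomised per arm; attrition of 10% cited from an earlier study.

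**Method.** Exact noncentral-t power, two-sided alpha 0.05.
- Paired, one group: noncentrality δ = d√n, df = n − 1.
- Independent, n per arm: δ = d√(n/2), df = 2n − 2.

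**Step 1: reproduce the plan's figures.** Paired test:
- d = 0.64: n = 21 gives 79.7%; n = 22 gives δ = 0.64 × √22 = 3.00 and 81.7%. The requirement is 22, as stated.
- d = 1.0: n = 9 gives 74.8%; n = 10 gives 80.3%. The requirement is 10, close to the stated fewer than 10.

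The plan does not name the G*Power procedure, so the paired origin is inferred.

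**Step 2: the planned between-arm test**, with 0.64 taken as the between-arm difference in SDs of the change score.

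| Per arm | Situation | Power |
|---|---|---|
| 22 | the stated size | 54.5% |
| 34 | 40 less 15% | 73.9% |
| 36 | 40 less 10% | 76.4% |
| 39 | | 79.7% |
| 40 | no dropout | 80.7% |

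At 40 per arm, δ = 0.64 × √20 = 2.86. The requirement is 40 per arm. Allowing for 10% dropout gives 40/0.9 = 44.4, so 45 per arm. The effect detectable with 80% power is 0.63 SD with 40 per arm and 0.67 SD with 36.

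**Step 3: if 0.64 is in raw-outcome SDs.** With equal variances, the SD of change is √(2(1 − ρ)) raw SDs, so the effect on the change score is 0.64/√(2(1 − ρ)). The plan gives no ρ; the values below are assumptions.

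| Assumed ρ | Effect on change score | Needed per arm | Power at 36 per arm |
|---|---|---|---|
| 0.3 | 0.541 | 55 | 61.9% |
| 0.5 | 0.640 | 40 | 76.4% |
| 0.6 | 0.716 | 32 | 84.9% |
| 0.7 | 0.826 | 24 | 93.3% |

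Power is 80% at 36 per arm when ρ is about 0.54, and at 22 per arm only when ρ is about 0.73.

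**Step 4: time in AF**, with 1.0 assumed to be the between-arm effect in SDs of change. With 16 per arm power is 78.1%, with 17 it is 80.7%, and with 36 it is 98.7%.

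**The case against.** **A within-group size suits one of the planned analyses.** The plan does include repeated measures ANOVA, and the 22 carries a repeated-measures label. That explains how the figure may have arisen. But the ANOVA is run inside each group and does not test the arms against each other, as the hypotheses require.

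**The origin of 22 is not certain.** A two-group repeated measures ANOVA on the between factor, with three visits, f = 0.32 and an assumed correlation of 0.3, needs 43 in total, or 44 with equal arms, which is also 22 per group. That is a fair caution. That test averages over visits including baseline, is not planned, and needs a correlation the plan does not give. Under either origin, 22 is not the size for the planned t-test at 0.64 SD of change.

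**The effect may be in raw SDs.** This stands as a limit. With a correlation of about 0.54 or more, the 10% allowance holds. The plan states neither scale nor correlation, so it does not make that case.

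**The consequence is modest.** This is also true. The drop is from 80.7% to 76.4%, on a secondary outcome, and the dropout sentence does not define adequate power. The only level the paragraph uses, however, is 80%.

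**The time-in-AF figure of 17 per arm has its own weakness.** It borrows a before-and-after effect and assumes normal data, and the plan does not show that percent of time in AF is normally distributed. So 17 can be stated only as an assumption.

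**Conclusion.** The concern holds. At 0.64, the stated 22 per group is the size for a one-group paired test. The planned independent t-test needs 40 per arm if 0.64 is the between-arm difference in SDs of the change score. On that reading the trial has 80.7% power for fitness with no dropout, 76.4% at 10% and 73.9% at 15%, so the calculation shown does not support the allowance of more than 10%.

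Two limits apply. The loss of margin depends on the scale of 0.64, which the plan leaves open. And nothing here shows that 40 per arm is too few for time in AF: if 1.0 is assumed as the between-arm effect, the allowance holds comfortably. The mismatch between calculation and test is firm. The paragraph should be corrected, but the design need not change.

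**What to change.** Keep 80 participants and rewrite the sample-size paragraph of section 5.4:

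- Replace the 22 per group with: *40 per arm for the between-arm independent t-test, assuming a between-arm difference of 0.64 SD of the change score*.
- Replace the dropout sentence with: *10% dropout leaves 36 per arm, which gives 76% power at 0.64, or 80% power for a difference of 0.67*.
- Replace the fewer-than-10 statement with: *17 per arm for the between-arm test, if the before-and-after effect of 1.0 is assumed to be the between-arm difference*.
- Say that both effects are before-and-after values used as assumptions, and which outcome each concerns: 0.64 for fitness, 1.0 for percent of time in AF.
- If the authors mean 0.64 in raw-outcome SDs, they should say so, give the assumed baseline to follow-up correlation, and state the size that follows. Only they can settle the scale.

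The cost is rewording one paragraph and a slightly less favourable stated power at 0.64. It takes no extra patients and no change of test. Keeping 80% power at 0.64 SD of change after 10% dropout would instead take 45 per arm, 90 in total. Keeping 80 means accepting about 76% for fitness in that case.
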